## Section 4 - Protocol Synopsis (Study 1)

### 4.1. Brief Summary

Current therapies for chronic psychotic disorders such as schizophrenia include antipsychotic medications, which do not significantly improve function or correct cognitive deficits in this disorder, and cognitive therapies, which produce only modest benefits to most patients. We hypothesize that medications that specifically target neurocognitive processes like attention and vigilance will significantly augment the clinical benefits of cognitive therapies in schizophrenia. Here, we will confirm that the pro-attention psychostimulant, amphetamine, enhances learning of an auditory processing task in a computerized targeted cognitive training (TCT) program in antipsychotic-medicated schizophrenia patients, and complete a randomized, double-blind clinical trial in antipsychotic-medicated schizophrenia patients, comparing TCT (30 sessions) plus amphetamine vs. TCT (30 sessions) plus placebo.

### 4.2. Study Design

#### 4.2.a. Narrative Study Description

Screened, eligible patients complete clinical, neurocognitive and functional measures and candidate biomarkers (EEG, QuickSIN, WIN). Aim 1 is completed in 2 tests, approximately 1 week apart. In Test 1, Sound Sweeps are tested after PBO for all subjects, who are then randomized to TCT+PBO vs. TCT+AMPH arms (n=27/arm) using stratified random sampling (over sex, age and high/low Test 1 APS learning) blind to arm identity, similar to our previous studies. Test 2 follows approximately 5-7 d later; this test is identical to Test 1, except that subjects receive their assigned study drug (PBO vs. AMPH (5 mg po)) 1 hour prior to Sound Sweeps. Tests 1 and 2 are used to assess target engagement (Aim 1: AMPH-enhanced APS learning) and AMPH effects on auditory discrimination (QuickSIN, WIN). Our design allows for 20% attrition from enrollment (n=69) to completion of target engagement testing (n=54). For Aim 2, TCT in these same subjects is scheduled 3 d/week (M-W-F) for 1-h/d, recognizing the need for flexibility (T-Th are "make-up days"), and continues until a subject completes 30-h (approximately 10-12 weeks). TCT is delivered by trained staff. 60 min prior to each TCT session, patients take either PBO or 5 mg AMPH, as per arm assignment. Patients and staff are blind to study arm; staff are blind to patients' baseline or post-intervention assessments. Outcome metrics assess symptom, neurocognitive and functional changes after 10, 20 and 30 TCT sessions, and 12 weeks post-TCT. Candidate biomarkers are re-tested after completion of 30 sessions of TCT.

#### 4.2.b. Primary Purpose

Treatment

#### 4.2.c. Interventions

Type	Name	Description
Behavioral (e.g., Psychotherapy, Lifestyle Counseling)	Targeted Cognitive Training	Thirty, one-hour sessions over approximately 10 weeks, of computerized cognitive training modules.
Drug (including placebo)	amphetamine	The pro-attentional medication, amphetamine (placebo vs. 5 mg) will be administered orally, 1 hour prior to targeted cognitive training, in a double-blind, randomized design.

#### 4.2.d. Study Phase

Phase 2/3

Is this an NIH-defined Phase III Clinical Trial?

Yes  No

#### 4.2.e. Intervention Model

Parallel

#### 4.2.f. Masking

Yes  No

Participant  Care Provider  Investigator  Outcomes Assessor

#### 4.2.g. Allocation

Randomized

### 4.3. Outcome Measures

Type	Name	Time Frame	Brief Description
Primary	Auditory Processing Speed (APS) learning	Test 1 and Test 2, one week apart	APS is measured before and after the TCT "Sound Sweeps" frequency modulation session, to determine the amount of "learning", based on the reduction in detection gap (ms). More learning (greater gain in processing speed) with amphetamine vs. placebo confirms target engagement, which is the primary outcome of Aim 1.
Primary	PANSS: Positive & Negative Symptom Scale total	baseline vs. post-TCT session 10, 20 and 30 (approximately 10 weeks), and 12 weeks post-TCT	TCT reduces both positive and negative symptoms of psychosis; we predict that amphetamine will augment these effects via enhanced TCT learning, detected by the PANSS. For this reason, and based on the need to limit total outcome measures, PANSS Total Score is the primary clinical outcome measure. Positive and negative symptom subscales, as well as PANSS factor-derived measures, will be assessed in exploratory analyses. Other secondary clinical measures will include: 1) Psychotic Symptom Rating Scales (assesses auditory hallucinations); 2) Young Mania Rating Scale; 3) Patient Health Questionnaire-9 (current depressive symptoms); 4) Abnormal Involuntary Movement Scale; 5) Columbia Suicide Severity Rating (C-SSRS); "Lifetime/Recent version" at screen; "Since Last Visit" at follow-up visits). The C-SSRS is a sensitive measure of suicidal ideation; any "yes" in C-SSRS prompts an immediate full evaluation/action plan by a study M.D.; and 7) AMPH Cessation Symptom Assessment
Primary	MATRICS Consensus Cognitive Battery Global Composite T-score (MCCB-C)	baseline vs. post-TCT session 10, 20 and 30 (approximately 10 weeks), and 12 weeks post-TCT	The MCCB measures 7 separable cognitive domains. Details are found in cited reports including past studies by the PI of drug effects on MCCB performance. Since the MCCB is assessed multiple times, alternate forms of the HVLT-R and BVMT-R are administered in counterbalanced order. MCCB Global Composite T-score (MCCB-C) is the primary neurocognitive outcome measure. Individual MCCB domain T-scores are used in secondary analyses to determine whether an overall effect is driven by specific aspects of neurocognition; specifically, TCT effects on verbal learning performance are known to be robust, and should be augmented by AMPH. Baseline MCCB performance (attention/vigilance subscale) will also be tested as a potential biomarker/ moderator of AMPH efficacy.
Primary	World Health Organization Disability Schedule (WHODAS 2.0)	baseline vs. post-TCT session 10, 20 and 30 (approximately 10 weeks), and 12 weeks post-TCT	Function will be assessed via the World Health Organization Disability Schedule 2.0 (WHODAS 2.0) at baseline, after sessions 10, 20 and 30, and week 12 post-TCT. WHODAS 2.0 is a 12-item patient-rated measure (< 15 min) using a 5-point Likert scale focusing on 6 domains: cognition, mobility, self-care, getting along with people, life activities, participating in society; it was recommended by the DSM-5 Task Force committee to replace the global assessment of functioning (GAF) scale.

NCT4414930: Pharmacologic augmentation of targeted cognitive training in schizophrenia
Statistical Analysis Plan

October 11, 2019

Statistical Design & Power

Design (see “Research Strategy”, Figure 7): Screened, eligible patients complete clinical, neurocognitive and functional measures and candidate biomarkers. In Test 1, all subjects are tested in Sound Sweeps after PBO, and then assigned to TCT+PBO vs. TCT+AMPH arms (n=27/arm) using stratified random sampling (over sex, age and high/low Test 1 (baseline) APS learning) blind to arm identity, similar to¹⁰⁷. Stratifying for baseline APS learning should increase the sensitivity of the primary target engagement metric. An example of a table for arm assignment is seen here:

Gender	Baseline	Age	Group								
Male	High	< 39	PBO	PBO	AMPH	AMPH	AMPH	AMPH	PBO	PBO	PBO
	High	≥ 39	PBO	AMPH	PBO	AMPH	AMPH	PBO	AMPH	PBO	PBO
	Low	< 39	AMPH	AMPH	PBO	PBO	PBO	PBO	AMPH	AMPH	AMPH
	Low	≥ 39	AMPH	PBO	AMPH	PBO	PBO	AMPH	PBO	AMPH	AMPH
Female	High	< 39	PBO	PBO	AMPH	AMPH	AMPH	AMPH	PBO	PBO	PBO
	High	≥ 39	PBO	AMPH	PBO	AMPH	AMPH	PBO	AMPH	PBO	PBO
	Low	< 39	AMPH	PBO	AMPH	PBO	PBO	AMPH	PBO	AMPH	AMPH
	Low	≥ 39	AMPH	AMPH	PBO	PBO	PBO	PBO	AMPH	AMPH	AMPH

Example of table for stratified random sampling, by gender, baseline APS learning (post-PBO) and age (based on approximate mean age (39 yo) of last 100 SZ patients tested in our program)

Test 2 follows approximately 5-7 days later. Tests 1 and 2 are used to assess target engagement (Aim 1: AMPH-enhanced APS learning) and AMPH effects on auditory discrimination. Our design allows for 20% attrition from enrollment (n=69) to completion of target engagement testing (n=54).

For Aim 2, TCT is scheduled 3 d/week and continues until a subject completes 30-h (approximately 10-12 weeks). 60 min prior to each TCT session, patients take either PBO or 5 mg AMPH, as per arm assignment. Patients and staff are blind to study arm; staff are blind to patients’ baseline or post-intervention assessments. Outcome measures are assessed after sessions 10, 20 and 30, and 12 weeks post-TCT. See “Research Strategy” for details.

General Statistical Approach: Hypothesis tests are 2-sided ($\alpha=.05$). Type I error is controlled by selecting optimal *a priori* targets for primary analyses; secondary analyses use false discovery rate corrections. When appropriate, missing data are handled via multiple imputation or full information maximum likelihood estimation. Expected drop-out rates and ways to minimize them are described in the parent application.

Differential drop-out rates from PBO vs. AMPH arms are monitored. Clinical follow-up is pursued with all patients exiting the study through post-TCT week 12.

Cohort differences: For between-subject contrasts (drug), baseline demographic, clinical, antipsychotic/anticholinergic load and performance differences are tested and used as covariates if indicated. Sex differences are tested for all measures.

Procedures for Alternative or Unexpected Results: Linear mixed-effects models allow for the analysis of all available data using an intent-to-treat approach. This approach, however, assumes that data are missing at random. A potential concern is nonrandom dropout, particularly when dropout is related to the (missing) outcomes; that is, not missing at random. To make the missing at random assumption more plausible, we will explore the use of auxiliary variables. Auxiliary variables are covariates that predict both dropout and outcomes. By adding auxiliary variables to our models, nonrandom dropout is corrected by conditioning treatment effects on the predictors of dropout.

Primary Efficacy Endpoint(s): Aim 1: Target engagement – APS learning will be significantly greater under AMPH vs. PBO conditions. Aim 2: Pilot trial - Compared to PBO arm patients, AMPH arm patients will exhibit greater clinical benefit, as indicated by one or more of the following: greater, faster or more durable improvements in PANSSt (reduced scores; see below, “Go/No-Go”), MCCBc (increased scores) or WHODAS (reduced scores).

Secondary Efficacy Endpoint(s): Aim 3: Biomarkers - baseline levels of specific neurocognitive or EEG-based measures, or changes in specific measures with initial AMPH exposure, predict greater sensitivity to AMPH-enhanced neurocognitive, clinical or functional gains over 30 sessions of TCT.

Analyses testing primary and secondary hypotheses will include all subjects' clinical, neurocognitive and functional assessments. Data from subjects who do not complete the full study are carried forward in an "intent to treat" design, and their data are analyzed using linear mixed models. Separate analyses will compare completion / drop-out rates across arms, as well as a 14-item 7-point Likert scale assessing treatment satisfaction.

Go/No-Go decision and primary and secondary endpoints

"Go/No-Go" decisions are based on traditional statistical significance (Aim 1) and effect sizes (Aim 2). Formal statistical testing is conducted using linear mixed-effects (LME) models; hypothesis tests are 2-sided ($\alpha=.05$). Model parameters are estimated via the R lme4 package and Cohen's d is estimated via the EMATools package. Type I errors are minimized by constraining the number of primary analyses; secondary analyses use false discovery rate corrections.

PANSSt scores will be assessed at specific intervals. **It is important to emphasize that the anticipated symptomatic gains will reflect an enhanced impact of TCT, rather than a direct therapeutic impact of AMPH (5 mg, 2-3 times per week).** Because TCT is associated with improvements in both positive and negative symptoms, our *a priori* hypothesis is that a PACT effect will be evident in both positive and negative symptoms. Hence, PANSSt is used as the primary metric of symptomatic gains. A greater reduction in PANSSt score will be detected using data from baseline through TCT 30h, by a significant main effect of group (arm) or a significant interaction of group x session, with post-hoc contrasts revealing significant group differences at TCT 30h. A faster reduction in PANSSt scores will be detected using these same data by a significant interaction of group x session and a significant group difference at a point prior to TCT 30h. A more durable reduction in PANSSt scores will be detected using data from TCT 30h through 12 weeks post-TCT, by a significant main effect of arm or a significant interaction of group x post-TCT day, with post-hoc contrasts revealing significant group differences 12 weeks post-TCT.

Comparable analytic approaches will be used for neurocognition (MCCBc) and function (WHODAS) as described in "Research Strategy". Data will be described as means with SEM. Tests for normalcy will be applied to all data and non-parametric comparisons will be used if normalcy is not demonstrated. The Analysis Set for these data will be all subjects who have completed 30h of TCT and post-TCT clinical, neurocognitive and function assessments. When appropriate, missing data are handled via multiple imputation or full information maximum likelihood estimation.

Secondary regression analyses assess the predictive value of putative biomarkers on clinical, neurocognitive or functional gains from the addition of AMPH to TCT. Future studies with larger samples will assess potentially more informative models, e.g. Path Analysis to study moderating effects of APS AMPH sensitivity and biomarkers on both indirect (moderated-mediation) and direct paths between treatment and outcome.

Power analyses

Consistent with the FOA, this study will adequately power tests of target engagement (Aim 1) for traditional significance, while the "Go" signal for therapeutic impact (Aim 2) is based on effect size ($d=0.5$). To detect target engagement with $d=0.5$, 80% power, $\alpha=0.05$, test-retest correlation =0.8, and a linear treatment effect, $n=27$ randomized participants are required per group. This is a very conservative estimate of d for target engagement, since empirically, d for target engagement with 5 mg amphetamine was 0.85 (Fig. 3A). A future Confirmatory Efficacy trial will be powered to apply more robust approaches to Aim 2, e.g. Path Analysis¹⁰⁸ to study moderating effects of APS AMPH sensitivity and biomarkers on both indirect (moderated-mediation) and direct paths between treatment and outcome.

Project Modification: Statistical Analysis Plan

The original study design included separate, parallel assessments of amphetamine (AMPH) (vs. placebo (PBO)) and memantine (MEM) (vs. PBO) effects on TCT-associated clinical, neurocognitive and functional gains. However, these designs pre-dated the pandemic, and between the date that they were proposed (10/2019) and the project start date (8/2020), our institution implemented a pandemic-related shut-down of clinical research activities. Even with the gradual resumption of research activities, recruitment lagged significantly behind target levels. As a result, we made several pragmatic adjustments to the original study designs:

1) Two separate but parallel protocols were approved by the UCSD IRB (protocols #191811, #201502) and posted on ClinicalTrials.gov. Due to the low recruitment numbers, the two parallel studies were combined and placebo groups were pooled, to yield a 3-group design 2) subject randomization changed from 1:1 to a 2:1 active : placebo ratio; and 3) adjustments were made to the planned statistical analyses, appropriate to the reduced sample size.

Based on known benefits of TCT in psychosis patients, no “placebo TCT” condition (e.g., video game) was included, for ethical and pragmatic reasons. Since all subjects received TCT, clinical gains over time in all groups might reflect, to some degree, the benefits of TCT. Pharmacologic augmentation by AMPH would only be evident if/when benefits in “TCT+active drug” groups exceeded those in “TCT+PBO” groups.

The primary goal of this study was to assess the clinical, neurocognitive and functional gains associated with the addition of AMPH to a full course of TCT. In total, there were 3 primary outcome measures and 5 secondary outcome measures. The primary clinical outcome measure was the Positive and Negative Symptom Scale (PANSS) total score; positive and negative subscale scores were secondary outcomes. Because they were highly correlated with total scores ($r=0.92$ at T_1), PANSS general scores are reported but are not outcomes. The primary neurocognitive outcome was the MCCB Composite Score. The primary functional outcome was the World Health Organization Disability Assessment Schedule (WHODAS 2.0, 12-item). Secondary clinical outcome measures also included the Patient Health Questionnaire (PHQ-9), the Young Mania Rating Scale (YMRS) and the Psychotic Symptoms Rating Scale (PSYRATS) hallucinations subscale.

Clinical, neurocognitive and functional outcome scores were treated as continuous variables and analyzed in three ways. First, they were submitted to linear mixed-effects (LME) models⁵⁹ for both between-group (interaction model: TCT+AMPH vs. TCT+PBO) and within-group (time model: baseline vs. P30, all groups) analyses. LME analyses included data from all randomized subjects (including those who did not complete 30 AT sessions) and modeled random intercepts to account for within-subject dependencies. Second, because sample sizes fell well below target levels, to test the hypothesis that active drugs would augment the impact of a 30-session course of TCT, the effect size (Cohen's d) of the change from baseline to P30 (“difference score”) was calculated for both between-group (TCT+AMPH vs. AT+PBO) and within-group (baseline vs. P30, all groups) comparisons. Between-group effect sizes were calculated as:

$$d = [(drug score T_1 - drug score P30) - (PBO score T_1 - PBO score P30)] / SD_{wav}$$

where SD_{wav} is the weighted average standard deviation. Within-group effect sizes were calculated as:

$$d = (score at T_1 - score at P30) / SD_{av}$$

where SD_{av} is the average of the standard deviations of the T_1 and P30 measures^{60,61}.

Third, to disentangle the salutary contributions of TCT alone vs. TCT+active drug to within-subject effect sizes, a “threshold” for positive active drug effects was set at “*d=0.4 above PBO values*”:

$$d(\text{active drug}) \geq d(\text{PBO}) + 0.4.$$

Because clinical gains from TCT+PBO were expected to be approximately $d=0.4$, this added threshold of “ $d=0.4$ above PBO” for drug-enhanced TCT meant that an estimated combined large effect size (at least $d=0.8$) would be required for a drug effect to be viewed as meaningful. Outcomes using thresholds from $d=0.2$ to $d=0.6$ were reported.

The use of effect size comparisons in addition to p-values is common in clinical trials research as a way to measure effects independent of sample size. It is particularly useful when, as in the current study, sample sizes fall below targets identified based on traditional power analyses. Effect size “thresholds” have been used by others to argue that TCT neurocognitive benefits exceed levels produced via PBO or practice effects (generally $d \approx 0.18$).

Indirect indicators of clinical impact included subject attrition, C-SSRS responses, treatment satisfaction and adverse events (AEs). AMPH group subjects were evaluated for abnormal involuntary movements (AIMS) and for deleterious effects of AMPH cessation (AMPH Cessation Symptom Assessment). Analyses included non-parametric (Chi-Square) and parametric (rmANOVA) tests.

Linear mixed-effects models for outcome measures included all subjects who were randomized; df were estimated using the Satterthwaite approximation. Between- and within-group effect sizes for clinical, neurocognitive and functional measures were calculated based on all subjects who completed 30 TCT visits and P30 testing (“completers”). For all analyses, α was set at 0.05; for analyses of the 5 secondary outcome measures, findings were also evaluated with a more restrictive alpha level (0.01) to correct for multiple comparisons.

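### The only allocation scheme shown, an example table in the SAP, is patterned on baseline APS learning; if it were used with few patients per stratum, arm would be associated with the factor it is meant to balance

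*SAP*

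**What the plan says.** In the SAP (Statistical Design & Power, Design), patients complete Test 1 on placebo and are then "assigned to TCT+PBO vs. TCT+AMPH arms (n=27/arm) using stratified random sampling", with strata "over sex, age and high/low Test 1 (baseline) APS learning) blind to arm identity". The reason for the third factor is given: "Stratifying for baseline APS learning should increase the sensitivity of the primary target engagement metric".

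The table that follows has eight rows (sex by High/Low baseline learning by age below 39 or not), each with nine assignments. It is called an example in the text ("An example of a table for arm assignment is seen here") and again in its caption: "Example of table for stratified random sampling, by gender, baseline APS learning (post-PBO) and age". Two rows show the structure: "High < 39 PBO PBO AMPH AMPH AMPH AMPH PBO PBO PBO" and, for men, "Low < 39 AMPH AMPH PBO PBO PBO PBO AMPH AMPH AMPH".

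The protocol's Aim 1 analysis paragraph relies on this stratification when it treats the arms as matched on Test 1 placebo performance. Target engagement is the first and indispensable Go criterion (protocol, Fig. 8). The SAP's paragraph on cohort differences makes covariate adjustment for performance conditional on a difference being found.

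The SAP's Project Modification section reports that "recruitment lagged significantly behind target levels". It says the ratio became 2:1 active to placebo, within a combined three-group design. Neither document states how sequences were generated, what block sizes applied, who held the list or how it was concealed, before or after that change.

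**The concern.** Stratified blocks protect balance because the leftover imbalance in part-filled strata has a random direction and tends to cancel. In this table it has the same direction in every stratum with the same learning level. The first patient in any High stratum gets placebo and the first in any Low stratum gets amphetamine. With short rows the leftovers therefore add up on baseline APS learning, the factor chosen to sharpen Aim 1.

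What is at stake is regression to the mean. Low Test 1 learners tend to rise at Test 2 and High learners to fall, with no drug effect. An excess of Low learners on amphetamine would favour amphetamine in a Test 2 versus Test 1 change contrast, and disfavour it in a comparison of Test 2 alone. The protocol describes both: the change form in the Aim 1 analysis, the Test 2 form under Specific Procedures (TCT). The pattern matters most when strata are thin, which is what a recruitment shortfall produces.

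**Working it through.** **The plan's own figure, to fix the scale.** For a change score with test-retest correlation r = 0.8, the SD is √(2(1 − 0.8)) = 0.632 in units of a single-test SD. The normal approximation gives n per arm = 2(1.960 + 0.842)² × 0.4 / 0.5² = 25.1, so 26. With the noncentral t, power is 0.798 at 26 and 0.813 at 27, so the stated 27 per arm is reproduced. The planned d = 0.5 is thus in single-test SD units, and the biases below are on the same scale.

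**Structure of the table** (P = placebo, A = amphetamine):

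- High, < 39, both sexes: PPAAAAPPP
- High, ≥ 39, both sexes: PAPAAPAPP
- Low, male < 39 and female ≥ 39: AAPPPPAAA
- Low, male ≥ 39 and female < 39: APAPPAPAA

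There are four distinct sequences in eight rows, and each Low row is the complement of a High row of the same sex. If first entries were independent and equally likely, all four High rows starting P and all four Low rows starting A would have probability (1/2)⁸ = 1/256. The first two entries of a row fix the other seven. Totals are 20 P/16 A in High and 16 P/20 A in Low.

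**Equal fill, k patients in every stratum.** The share is the proportion of an arm who are Low learners.

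| k | Patients | Low share, AMPH | Low share, PBO | Difference |
|---|---|---|---|---|
| 1 | 8 | 4/4 | 0/4 | +1.00 |
| 2 | 16 | 6/8 | 2/8 | +0.50 |
| 3 | 24 | 8/12 | 4/12 | +0.33 |
| 4 | 32 | 8/16 | 8/16 | 0 |
| 5 | 40 | 8/20 | 12/20 | −0.20 |
| 6 | 48 | 10/24 | 14/24 | −0.17 |
| 7 | 56 | 12/28 | 16/28 | −0.14 |
| 8 | 64 | 16/32 | 16/32 | 0 |
| 9 | 72 | 20/36 | 16/36 | +0.11 |

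**Random arrival.** Assumptions: eight equally likely strata, and rows reused beyond nine patients. The mean share difference D is +0.37 at 16 patients, +0.16 at 24 (positive in 95% of simulated fills), +0.06 at 30 and about −0.01 at 54. Independent permuted blocks of 4 average zero at every size. At 54 patients the average stratum holds 54/8 = 6.75.

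**Bias with no drug effect.** Assume a median split of a normal score, so the High and Low means lie 2 × 0.798 = 1.596 SD apart. An excess D of Low learners lowers the amphetamine arm's Test 1 mean by 1.596D, and a fraction r of that deficit persists at Test 2.

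- Change contrast: 1.596 × D × (1 − r). At r = 0.8 this is 1.596 × 0.37 × 0.2 = +0.12 SD at 16 patients and 1.596 × 0.16 × 0.2 = +0.05 SD at 24.
- Test 2 only: −1.596 × D × r. At r = 0.8 this is −1.596 × 0.37 × 0.8 = −0.47 SD at 16 and −1.596 × 0.16 × 0.8 = −0.20 SD at 24.

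Relative to the planned 0.5, the change-contrast bias is 0.12/0.5 = 24% at 16 patients and 0.05/0.5 = 10% at 24. As a sensitivity value not taken from the documents, r = 0.5 gives change-contrast biases of 0.30 and 0.13 SD.

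**The case against.** The strongest reply is that the SAP labels the table an example twice and names the method as stratified random sampling with concealment of arm. A reader might infer from the pattern that patients were allocated non-randomly. The documents do not support that: an illustration is not the operative list, and the two-arm 1:1 grid cannot have served the later 2:1 three-group design. How many patients, if any, were assigned under 1:1 is not stated. This stands in full, and it is why the point is conditional.

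A reader might also infer that arm and learning stay confounded until the strata are full. They do not. Balance is exact at 4 and 8 per stratum, the direction reverses at 5 to 7, and the average at 54 is about zero.

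A third inference is that staff could foresee assignments. That needs the list itself, or the pattern plus the earlier arms in a stratum. Patients and staff are stated to be blind, both arms take a pill, and the High/Low label is known only after consent and Test 1. The protocol does provide for an unblinded staff member and for breaking the blind in pregnancy, so the route exists but is narrow.

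On size, the bias in the change contrast is modest at the plan's own correlation. Proper methods also leave chance imbalance. At 24 patients the mean absolute share gap is about 0.17 for this table, 0.09 for permuted blocks of 4 and 0.17 for unstratified randomisation. The difference is that the table's gap almost always points the same way.

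Finally, both documents foresee dealing with baseline differences. The SAP does so only where a difference is judged to call for it, and with few patients a test for baseline difference can miss a gap of this size. The modified SAP's three primary outcomes are PANSS, MCCB and WHODAS, so the computed bias concerns Aim 1 and not those endpoints.

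**Conclusion.** The point holds conditionally. The sole allocation scheme shown ties arm to baseline APS learning, and if it or its pattern were used, the two would be associated while strata hold about three or fewer patients. The sizes above rest on equally likely strata, a median split of a normal score (no High/Low cut-off is given) and, for the main figures, the plan's correlation of 0.8. The bias is small to moderate for the change contrast and large for a Test 2-only contrast, and it averages about nothing at the planned enrolment.

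This is more than a reporting gap. The illustration works against the stated purpose of the stratification, the Aim 1 analysis leans on the resulting match, and no other method or guaranteed adjustment is written down. It is not evidence that the trial's actual allocation was flawed. It should be corrected, but it does not by itself undermine the design.

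**What to change.** 1. Replace the example with independently computer-generated, randomly permuted blocks of varying and undisclosed size within each stratum, for both the 1:1 and the 2:1 ratio. The pharmacist or designated unblinded staff should hold the lists. Do not print arm-labelled sequences in the SAP.
2. State whether the example table was used for any patient, and if so for how many and in which strata. The Project Modification section is written in the past tense. For patients already assigned, the remedy is therefore to document the list and concealment actually used.
3. Make Test 1 APS learning a planned covariate in the between-arm Aim 1 contrast, regardless of any observed difference. Under a linear relation this removes the expected bias in either form of the contrast. It also helps power: the residual SD becomes √(1 − 0.8²) = 0.6 instead of 0.632, and power at 27 per arm rises from 0.81 to 0.85.

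The cost is a regenerated list where assignment is still open, a few SAP sentences, and one covariate that is already collected.

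### The SAP says Type I error is controlled for the primary analyses, but nothing adjusts across the three Aim 2 primaries; with no true effect, at least one reaches p<0.05 in about 11–14% of trials (5.5–7.4% in favour of AMPH)

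*SAP*

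**What the plan says.** The SAP, General Statistical Approach, sets two-sided tests at 0.05 and states "Type I error is controlled by selecting optimal" targets in advance for the primary analyses. Only secondary analyses get a false discovery rate correction. The Go/No-Go section, like the protocol's Data Analysis section, makes a weaker statement: "Type I errors are minimized by constraining the number of primary analyses".

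Under Primary Efficacy Endpoint(s), the SAP counts Aim 2 benefit "as indicated by one or more of the following: greater, faster or more durable improvements in PANSSt", MCCBc or WHODAS, and gives the favourable direction for each measure. One success is enough.

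The Project Modification keeps this structure: "In total, there were 3 primary outcome measures and 5 secondary outcome measures". The primaries are PANSS total, MCCB composite and WHODAS 2.0. Alpha is 0.05 for every analysis. The only extra step is a second look at the five secondary outcomes at 0.01, to allow for multiple comparisons.

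Separately, the protocol (Outcome and Go Decisions) and the SAP (Go/No-Go and Power analyses) base the Aim 2 Go decision on effect size and reserve significance testing for Aim 1.

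**The concern.** Choosing a small number of targets in advance limits how many tests are run. It does not hold the joint error rate at 5% when there are three tests and any one of them may be taken as showing benefit. That needs an alpha split, a testing order, a gatekeeping rule or adjusted p-values, and neither version of the plan contains one for the three Aim 2 primaries. The contrast within the modified plan is marked: the five secondaries get a corrected level and the three primaries do not.

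The p-values will still be produced and read. The Go/No-Go section describes greater, faster and more durable gains in terms of significant effects, and the Project Modification runs mixed models on all three primaries at 0.05. A reader who trusts the assurance in General Statistical Approach could take the appearance of one significant primary among three as an event with a 5% chance under no effect. For any single outcome named beforehand 5% is right. For at least one of three it is not.

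**Working it through.** **Figure in the documents.** Neither document states a joint error rate for the primaries, so there is none to reproduce. The correction for the secondaries can be checked: 0.05/5 = 0.01, and for five independent tests 1 − 0.99^5 = 4.9%. The plan thus holds that family near 5%.

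**Inputs.**
- Three Aim 2 primaries (SAP, Project Modification).
- Alpha 0.05, two-sided, for each (SAP, General Statistical Approach and Project Modification).
- Success on one or more (SAP, Primary Efficacy Endpoint(s)).
- One between-group test per outcome, baseline to P30 (assumption, following the modified plan).
- Correlation between outcomes: not given in the documents, so shown as a range.

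**Independent outcomes.**
- At least one two-sided p<0.05: 1 − 0.95^3 = 14.3%.
- At least one in favour of AMPH: 1 − 0.975^3 = 7.3%.

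**Correlated outcomes.** Four million draws of three equally correlated null z statistics gave:

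| Assumed correlation | Any p<0.05, two-sided | Any in favour of AMPH |
|---|---|---|
| 0 | 14.3% | 7.3% |
| 0.2 | 14.0% | 7.0% |
| 0.3 | 13.6% | 6.8% |
| 0.5 | 12.5% | 6.3% |
| 0.7 | 10.9% | 5.5% |
| 0.9 | 8.4% | 4.2% |
| 1.0 | 5.0% | 2.5% |

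**Small samples and unequal allocation.** A separate simulation used t tests on three correlated change scores, 200,000 null trials per setting. With two visits and complete data this is the same as the group-by-time test in a random-intercept mixed model. At a correlation of 0.3 it gave 13.7–13.8% two-sided and 6.8–6.9% in favour of AMPH. Over correlations from 0.7 to 0 it gave 11–14% and 5.5–7.4%. Results were alike at 18/18, 27/27 and assumed 2:1 splits of 20/10 and 12/6, so neither the change in allocation nor the reduced sample alters the conclusion.

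**With an adjustment.** At 0.05/3 = 0.0167 each, independence gives 1 − (1 − 0.0167)^3 = 4.9%. Holm gave 3.9–5.0% over the same correlations.

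**The case against.** The strongest reply is that no stated decision rests on these p-values. This is a pilot. The protocol says openly that Aim 2 is judged on effect size because of the funding call and the limited sample, with a confirmatory trial to follow. It also requires Aim 1 significance and no significant excess of adverse effects. It discloses the multiplicity too: it notes that looking at rate and durability triples the primary analyses, and for that reason keeps one primary per domain. All of this stands, and it limits the weight of the point. It does not make the sentence in the SAP accurate. Nor does the Aim 1 requirement limit error across the three Aim 2 outcomes when target engagement is real, and the Project Modification does not restate it.

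A reader might infer three stronger things.
- *That the chance of a false Go is 14%.* The documents do not support this, because the Aim 2 Go criterion is an effect size and not a p-value.
- *That the chance of a false claim of AMPH benefit is 14%.* The endpoint definition is directional. About half of the 14% is AMPH looking worse, so the relevant figure is 5.5–7.4%.
- *That the rate is higher still, because each outcome can succeed by being greater, faster or more durable.* Those routes belong to the October 2019 plan. The Project Modification's analysis description no longer lists them, so no figure for them is claimed here.

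It is also fair to say that formal adjustment across three domain-specific outcomes in a pilot is partly a matter of preference. That is why the remedy below is about wording.

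**Conclusion.** The point holds as a mismatch between a stated property and the tests. The SAP says Type I error is controlled for the primaries, yet any one of three unadjusted tests at 0.05 may indicate benefit. Under no effect the chance of at least one two-sided p<0.05 is about 11–14%, and of at least one in favour of AMPH about 5.5–7.4%.

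These figures assume one between-group test per outcome at P30 and a between-outcome correlation from 0.7 to 0. Stronger positive correlation would lower them, to 8.4% and 4.2% at 0.9. The absence of any adjustment is certain from the text; only the exact rate depends on the correlation. The effect-size Go rule is untouched. What changes is how much a lone primary p<0.05 may be taken to show.

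**What to change.** In the SAP, General Statistical Approach, replace the statement that Type I error is controlled with:

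> No adjustment is made across the three Aim 2 primary outcomes; their p-values are descriptive, and the chance of at least one p<0.05 under no effect is up to about 14% (about 7% in favour of AMPH).

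The clause on secondary analyses can stay. The weaker wording in the Go/No-Go section and in the protocol can also stand. This costs no data and no power.

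Holm-adjusted p-values for the three P30 between-group tests may be reported alongside as a supplement. The Project Modification is written in the past tense and reports an observed correlation (0.92), so they must be labelled post hoc if outcome data by arm have been seen. Holm is better as a supplement than as the sole criterion because it is expensive in a small pilot. For one outcome with a true d of 0.5 on the change-score SD, power at the first Holm step falls from 31% to 17% at 18 per arm, and from 44% to 27% at 27 per arm.
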